4.1 STUDY INTERVENTIONS

STUDY DRUG: Avmacol Extra Strength capsules

IND # 158689

IND HOLDER: [name]

For Phase I, we will only use Avmacol ES, no placebo, to determine the PK of Avmacol ES in CKD to guide the dose used for Phase II.

Nutramax Laboratories, Consumar Care, Inc., will provide Avmacol ES capsules free of charge in bottles shipped directly to University of Rochester Medical Center (URMC) Clinical Research

Page 2 of 13

Pharmacy Investigational Drug Services (IDS). The IDS will store, monitor, and dispense the drug directly to subjects. Data from the study will be shared with Nutramax.

It should be noted that, compared to control, SFN at "low dose" or 0.5 μM concentration, ex vivo, is able to induce expression of the genes in human peripheral blood mononuclear cells (PBMCs) that encode the enzymes AKR1C1 and NQO1 that play a role in reducing radical species 5. Higher doses of 2 µM and 5 uM of SFN induce higher expression of AKR1C1 and NOO1, as well as HO-1. Other human trials with SFN have reported higher peak plasma concentrations of 1-2 µM ⁶.

GSTM1 genotype will first be determined for the PK analysis to assess whether the genotype influences

drug metabolism. Stratified by GSTM1 group, patients will be assigned randomly to 2 or 4 Avmacol Extra Strength tablets once a day, taken orally with food, as depicted in **Table 1**. The groups are categorized into *GSTM1* null (GSTM1 (0/0) or GSTM1 non-null (GSTM1 (1/1) or (1/0)) genotype based on the dominant model we observed in AASK and ARIC cohorts ^{2,3}.

Table 1: Number of Avmacol Extra Strength Tablets Once a Day				
GSTM1 Genotype	2 Tablets	4 Tablets		
GSTM1 (1/1 or 1/0)	6	6		
GSTM1 (0/0)	6	6		
0071117 (0/0)				

Between 800-900 patients are seen monthly in the URMC Kidney Clinic in AC-3 and Highland Hospital. Among these patients, ~ 60% have CKD Stage 3 or 4, and $\sim 40\%$ of the total patients are African American.

Table 2	Prevalence		
GSTM1 Genotype	Caucasians	African Americans	
GSTM1 (1/1 or 1/0)	50%	73%	
GSTM1 (0/0)	50%	27%	

The null genotype is quite common in human populations, with 50% Caucasians and 27% African Americans being homozygous for the GSTM1 (0/0) allele (see Table 2 for prevalence of GSTM1 genotypes) 7. We saw similar prevalence of genotypes in AASK and ARIC 2-4. Therefore, we do not anticipate difficulty identifying those with null versus non-null genotypes.

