4.2 SUBJECT POPULATION

Page 3 of 13

We will enroll 24 adult patients followed in the Kidney Clinic in AC-3 with chronic kidney disease. Evaluable subjects who withdraw from the study will be replaced to meet the enrollment goal. We will recruit patients of any gender, race, and socioeconomic status.

Vulnerable Subjects: We do not plan to include vulnerable subjects such as children, pregnant women, fetuses, or prisoners. Employees (physicians/fellows) will be assured that taking part in research is not a part of their duties, and refusing to participate in the study will not affect their job. To ensure their autonomy, the research coordinator (rather than the PI) will consent them.

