8. STUDY PROCEDURES

Page 5 of 13

SCREENING PROCEDURES:

Avmacol ES has not been tested in patients with CKD. Since sulforaphane (SFN) and its metabolites are cleared by the kidney, to establish a safe dose for our study participants, for Phase I of the study, we will first perform PK analysis in CKD Stage 3B to 4 patients with eGFR between 25 - 45 mL/min/1.73m² who meet the inclusion criteria below. The eGFR result should be within a 2 week window at the time of screening. If eGFR testing was performed longer than 2 weeks, the research coordinator will reach out to the patient's provider to ask for repeat testing.

Our research coordinator will use eRecord EMR to screen patients for enrollment based on inclusion and exclusion criteria listed above in #5. Each week, the research coordinator (RC) will screen subjects scheduled to visit to the Kidney Clinic in the upcoming 1 to 2 weeks for enrollment. The RC will discuss with [name], who will make the final decision for inclusion and exclusion. If eligible and after subject consent is obtained:

A total of 2 in-person study visits will occur for the Phase I study. The first visit (AC3 or Highland Hospital) is expected to last for 1 hour. The second visit will only occur at the Clinical Research Center in Strong Memorial Hospital (SMH) and will take place on day 7 of taking the study drug and is expected to last up to 9-hours to allow biospecimen collections at 5 separate intervals.

RANDOMIZATION:

As noted in Section 4.1 Study Interventions, groups will be stratified by GSTM1 group, patients will be assigned randomly to 2 or 4 Avmacol Extra Strength tablets once a day, taken orally with food, as depicted in Table 1 (below). The groups are categorized into GSTM1 null (GSTM1 (0/0) or GSTM1 nonnull (GSTM1 (1/1) or (1/0)) genotype based on the dominant model we observed in AASK and ARIC cohorts. We do not anticipate difficulty obtaining the different genotype groups, as 75% of Caucasians are either GSTM1 (1/1) or (1/0), and 25 % are GSTM1 (0/0). Approximately 65% of patients in our Kidney Clinic are Caucasians. In African Americans/blacks, approximately 25% are GSTM1 (1/1), 50% are GSTM1 (1/0), and 25 % are GSTM1 (0/0). Approximately 30% of patients in our Kidney Clinic are African Americans. Randomization will be performed by the IDS who will be provided the patients' eGFR and GSTM1 genotypes. Since this is a PK study, the investigators will not be blinded to the randomization.

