- Harmonize the study data elements and variables from clinical and laboratory and biochemical data
- 5. Validate data quality and perform cleaning process.
- 6. Work closely with the PI and clinical investigators to determine appropriate statistical methods and machine learning algorithms for the clinical hypotheses. Cutting-edge statistical methods and innovative data science tools will be considered or adopted.
- 7. Prepare the analytical datasets and perform pre-stated statistical analyses.
- 8. Prepare the final results for manuscript writing and submission, conference presentations and publications.

The data for safety and feasibility assessment will be summarized descriptively with respect to adverse events and compliance with Avmacol ES intake. The group-specific data will be summarized and reported as mean \pm SD for continuous measures and as frequency and percentage for categorical measures and their differences will be compared using two-sample t-tests or Chi-square test.

18. PI oversight for multi-site research

The UR PI will be responsible for the following:

- A. Communication: The UR Pi will notify the Site PI of the RSRB site approval and provide site approval letter as well as copies of the most current version of the study materials via email. The UR PI is responsible throughout the course of the study to provide all modified documents and IRB approval letters to UVA site PI.
- B. Supervision of study activities at the site: The UR PI will conduct regular meetings with the site PI to review study activities. Meetings will occur every 3 months or sooner as soon as any issue arises by zoom. During the meeting, the UR PI will troubleshoot study-related issues, answer study-related questions, and provide verbal/written direction for all study activities. Meetings will be documented via meeting minutes in the regulatory binder.
- C. Training: The UR PI will ensure that all study personnel have completed required institution-specific and protocol-specific trainings and that these trainings are documented appropriately via CITI certification. When study personnel are added/removed, the UR PI will ensure UVA submits these changes to the local IRB for institutional review and approval. If applicable, these changes will be appropriately documented on the Delegation of Responsibilities Log.

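### Section 17 sets no confidence limit on the adverse-event rate at either dose, and the between-group tests it names cannot supply one

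*Combined protocol and SAP*

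**What the plan says.** Section 8 (Screening procedures) notes that the product has not been tested in CKD and that sulforaphane is cleared by the kidney. It says the PK analysis comes first "to establish a safe dose for our study participants, for Phase I of the study".

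Section 4.1 rules out an untreated comparator: "For Phase I, we will only use Avmacol ES, no placebo". Within genotype strata, "patients will be assigned randomly to 2 or 4 Avmacol Extra Strength tablets once a day", and Table 1 puts 6 patients in each dose-by-genotype cell.

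Section 17 has two sentences on analysis of the data. The first covers safety: "The data for safety and feasibility assessment will be summarized descriptively with respect to adverse events and compliance with Avmacol ES intake". The second says group-specific data will be given as mean and SD or as frequency and percentage, and "their differences will be compared using two-sample t-tests or Chi-square test". It does not say whether the groups are doses or genotypes, or whether the tests cover adverse events. It states no alpha, confidence interval, upper limit or acceptable event rate.

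Section 4.1 chooses the Phase II dose by PK similarity to non-CKD patients and calls Phase II the safety and efficacy study. Sections 4.2 and 13 provide for replacing participants who withdraw, and section 4.1 provides for halving the dose after side effects.

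**The concern.** Phase I will be the first safety experience with this product in CKD, and its reader will want to know what event rate the data can exclude at the dose carried forward. A between-group test answers a different question, namely whether one group on active drug differs from another. If both doses cause the same harm there is no difference to find, and more patients would not change that.

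The likely result is a handful of events. The plan as written would then report counts, percentages and possibly a p-value, with nothing to show how little 12 patients per dose can exclude. The DSMB and the Phase II planners would have to work out that bound themselves, and could be misled if replaced participants had dropped out of the denominator.

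**Working it through.** **Inputs from the documents.** 24 patients (section 4.2); four cells of 6 (Table 1); no placebo (section 4.1). **Assumed, because not stated:** two-sided alpha 0.05, and all event rates used for power.

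**Group sizes.** 4 × 6 = 24, which reproduces the enrolment figure. Each dose has 6 + 6 = 12 and each genotype group has 6 + 6 = 12, so either reading of the groups gives 12 v 12. The documents give no power or precision calculation to reproduce.

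**What the data can exclude.** The exact (Clopper-Pearson) one-sided 95% upper limit p for x events in n solves P(X ≤ x | n, p) = 0.05. With x = 0 this is p = 1 − 0.05^(1/n). No event rate has to be assumed.

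| Observed | One-sided 95% upper limit | Upper end of two-sided 95% interval |
|---|---|---|
| 0/6 (one Table 1 cell) | 1 − 0.05^(1/6) = 39.3% | 45.9% |
| 0/12 (one dose) | 1 − 0.05^(1/12) = 22.1% | 26.5% |
| 1/12 | 33.9% | 38.5% |
| 2/12 | 43.8% | 48.4% |
| 0/24 (pooled) | 1 − 0.05^(1/24) = 11.7% | 14.2% |

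**Harm common to both groups.** With a true rate of 30% in each group, exact enumeration of two binomials with n = 12 gives a Pearson Chi-square rejection rate of 4.9% (Fisher 1.7%). The test is non-significant about 95% of the time. That is its size, so a larger sample would not help.

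**Harm that differs between groups.** Power at 12 v 12 by exact enumeration:

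| Assumed rates | Pearson | Fisher |
|---|---|---|
| 10% v 30% | 20% | 10% |
| 10% v 40% | 39% | 23% |
| 10% v 50% | 60% | 43% |
| 10% v 60% | 79% | 64% |

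An observed 0/12 v 3/12 gives Chi-square = 24 × (0×9 − 12×3)² / (12 × 12 × 3 × 21) = 31,104 / 9,072 = 3.43, below the critical value of 3.84 (p = 0.06). Against 0/12, significance needs 4/12 (Pearson) or 5/12 (Fisher).

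**Why the denominator matters.** Suppose one participant at a dose withdraws for a side effect and is replaced by one who has no event. If the first is dropped, the dose shows 0/12, limit 22.1%. If all dosed participants are kept, it shows 1/13. The limit then solves (1 − p)^13 + 13p(1 − p)^12 = 0.05, which gives p = 31.6% (0.0071 + 0.0429 = 0.05).

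**The case against.** The strongest reply is that section 17 assigns safety data to descriptive summary. The tests sit in the next sentence and attach to groups it does not define. Genotype is a fair reading, since section 4.1 uses the word groups for the genotype categories and section 4 states a genotype hypothesis on bioavailability. A reader might infer that the plan's safety inference is a dose-difference test; the text does not say so. This stands, and the point does not depend on it. If the tests do cover safety, they cannot bound harm under either reading. If they do not, safety has no inferential summary at all.

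A reader might also infer that a non-significant result will be taken as proof of a safe dose. The documents do not support that. No sentence links the tests to a safety conclusion, the section 8 phrase describes the purpose of PK analysis, and the dose is chosen by PK match.

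Nor does patient protection hang on a p-value. Section 4.1 has individual dose-reduction and stopping provisions, section 13 has withdrawal criteria, section 8 has symptom questionnaires and a follow-up call, and the DSMB reviews adverse events and is convened for any serious one. All of these act on single events. None of them sets a rate threshold or states what rate the data can exclude.

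Finally, it would be too strong to say that the test misses most relevant harm. The documents define neither relevant harm nor event rates, and power rises to 79% (Pearson) or 64% (Fisher) at an assumed 10% v 60%.

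**Conclusion.** The concern holds as a gap in the safety summary: no precision or upper limit is planned for adverse-event rates by dose, and the only tests named cannot provide one. The size of the gap does not rest on assumed rates. A dose group with no events in 12 still allows rates up to 22%, and two such groups pooled allow 12%. The power figures do rest on assumed rates and alpha, and are illustrative only.

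This is not a fault in the dose-selection rule or in the monitoring of individual patients. The change is worth making because it costs almost nothing and alters what Phase I can say about safety.

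**What to change.** In section 17:

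1. Define the groups, stating which comparisons are by dose and which by genotype.
2. For adverse events, dose reductions and side-effect withdrawals, replace the between-group test with the proportion at each dose and the pooled proportion, each with an exact (Clopper-Pearson) one-sided 95% upper limit. Add the risk difference between doses with a 95% interval.
3. Count every participant who took at least one dose, by assigned dose, including those later replaced (sections 4.2 and 13) or dose-reduced (section 4.1).
4. State that the limits apply to 7 days of dosing, whereas section 2 plans 6 months of treatment in Phase II, and that a non-significant difference is not evidence of safety.

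The cost is a few lines of text and trivial analysis of data already being collected. It needs no extra patients and changes no clinical rule. The downside is that the safety statement will look less favourable: no events in 12 would be reported with its 22% limit attached.
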